2.2 Study Rationale

Almost all (98%) community-living older adults with ADRD rely on the help of family caregivers.(28, 29) The societal cost of ADRD is exceedingly high due to heavy reliance on family, particularly at the end of life.(1, 30) Family caregivers of persons with ADRD provide hands-on care, coordinate information and care, and serve as surrogate decision-makers when persons with ADRD can no longer make decisions themselves.(28, 29) Family caregivers of persons with ADRD actively participate in primary care visits,(31-33) and may inhibit or facilitate ACP.(24, 34, 35) Barriers related to lack of knowledge, fear, and reluctance are remediable with support and education.(12, 36) A meta-analysis of 12 ACP interventions in community settings reported a statistically significant pooled effect size of 1.92 for advance directive completion at 1-18 months follow-up.(36) Caregiving burden, stigma, and illness characteristics amplify the difficulty and importance of ACP discussions for older adults with ADRD.(24, 37) The few ACP interventions that specifically address the needs of persons with ADRD have been undertaken in nursing homes.(36, 38, 39) The lack of accuracy of advance directive documentation in the electronic health record is well-recognized. The level of accuracy at our two health system partners is not now well understood. Both JHCP and MedStar Health seek to conduct an audit of data quality relating to the primary outcome to assess data accuracy prior to the launch of the trial. Simulations using standardized patients are a high-fidelity, low-stake opportunity to evaluate knowledge, skills, and competencies for behavioral attributes (e.g., communication skills) associated with high-quality healthcare delivery. Simulation trainings have been used to assess caregivers' and clinicians' confidence, empathy, and knowledge of topics related to dementia care. Simulation trainings have also been used to routinely assess how well members of a care team adhere to elements of an intervention and serve as an extension of training role plays to ensure that skill decay is minimized for staff with direct interaction with patients. The goal of simulation is not only to assess skills and competency, but also to aid staff in identifying opportunities for improvement to ensure patient safety. Utilization of simulated patients in SHARING Choices adds to the literature on how simulation training can be used to evaluate readiness and aptitude of staff engaging in methodologically rigorous ACP conversations with patients with ADRD and their caregivers. Katwa et al. used a simulation training for care home staff to increase knowledge about advance care planning, noting that simulation training could be used "to test the strength of implementation of policies and standard operating procedures" and to "check for compliance" (30). The study will evaluate adherence to the Respecting Choices ACP framework (*see section 4.1 below*), quality of delivery, and areas for further improvement that may impact study outcomes. Simulation activities for this trial will pose minimal risk to facilitators, offer opportunities for debriefing with expert faculty to support management and emotional response to encounters including just-in-time coaching to reinforce exemplary skills.

3 **STUDY DESIGN**

This study will evaluate the implementation effectiveness of SHARING CHOICES to increase the rate of advance directive documentation and improve end-of-life outcomes using a pragmatic, cluster randomized trial design. Outcomes from data collected in routine clinical care will be aggregated at the practice level in up to 100 diverse primary care practices from 2 health systems. Practices randomized to SHARING CHOICES will have information electronically sent or mailed to their patients. SHARING CHOICES practices will have access to a trained ACP facilitator who will be available to engage the patients and their healthcare agent in ACP discussions when desired. We will evaluate effectiveness of SHARING CHOICES by analyzing data collected for non-research purposes from the electronic health record (EHR). To facilitate understanding of how to operationalize the primary endpoint of advance directive documentation and with support from JHCP and MedStar Health leadership, we will perform an advance directive audit within the EHR to characterize the quality of data existing in the electronic health record across 19 JHCP and 35 MedStar clinics prior to the launch of the intervention. To ensure ACP facilitator implementation fidelity to the methodological training components of the ACP conversation, facilitation staff will be evaluated via supervised interactions with simulated patients (**D1, D2, D3**).

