To evaluate ACP facilitator implementation skill and competency to perform ACP conversations, each facilitator will do two case-based simulations with standardized patients (SPs) via teleconference (**D2, D3**). The first case is an SP with mild cognitive impairment and the second case involves an SP with dementia and their caregiver. Each simulation will include a 10-minute pre-brief session (**D1**) to orient the facilitator to the simulation and a 30-minute simulation with the SPs followed by a 15-minute debrief to identify adherence to the intervention, quality of delivery, and areas for further improvement. Adherence will be measured using the Advance Care Planning (ACP) Facilitator Evaluation Checklist, a short fidelity instrument adapted from SHARE (IRB00242431) and Respecting Choices® to evaluate communication skills and the key elements in an ACP conversation (**E1, E2**). The results will also be used to inform additional booster training for facilitator staff.

The overall duration of patient follow-up will be 12 months as measured from the most recent primary care appointment date when the patient is sent the SHARING CHOICES materials. The overall study duration is expected to be 18 months.

Sample Size and Population

We will engage a diverse mix of practices by geographic region (urban, suburban, rural) and size. The unit of randomization for this study is the primary care practice. Study participants will include all primary care patients age 65 and over, including those with ADRD and their family at up to 100 primary care practices. We anticipate that 9,200 of 87,000 of older patients will have a diagnosis of ADRD, and 7,000 will die within 12 months of study entry and be eligible for the potentially burdensome end-of-life care outcomes.

STUDY TEAM ROSTER

Principal Investigator: **[name]**

[name]
[name]
[contact]
[contact]

Medstar Site Principal Investigator: [name]

MedStar Institute for Quality and Safety
[name]
[name]
[name]
[contact]
[contact]

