4 IDENTIFICATION OF PRIMARY CARE PRACTICES

(1) Practice Identification: Practices will be included from two health systems: Johns Hopkins Community Physicians (JHCP) and MedStar Health. For the purposes of this study, primary care is defined as adult internal medicine, family medicine, and geriatric medicine. Practices will be randomized to SHARING CHOICES or usual care, stratified by health system and balanced on clinical characteristics.

4.1 Facilitator Identification:

Facilitators will be social workers or trained lay facilitators who will be employees of the Johns Hopkins School of Medicine or JHCP. Facilitators will be provided 15 hours of initial training, and biweekly, one hour training sessions prior to the start of the trial. Training will include all components of SHARING CHOICES, including: certification in the Respecting Choices ACP curriculum, with specific attention to working with patients with ADRD and families; documenting and uploading advance directives; patient and family portal registration and use; ADRD resources; and facilitating family communication with the agenda-setting checklist. Training will be delivered and reinforced using traditional didactics, case scenarios and video conversations, and modeling and mentored role play (see Attachment A4 for the training agenda). ACP facilitator staff will participate in two 55-minute simulation sessions to assess training fidelity, communication skills and the key elements of an ACP conversation.

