6 STUDY PROCEDURES

Audit

Preparatory to the detailed audit, an exploratory analysis will be performed using Natural Language Processing (NLP) to determine the number of existing patient records with a textual reference to advance care planning processes and documentation. This analysis will not include patient identifiers. NLP will be used to identify the proportion of patients whose charts do and do not have official documentation of an advance directive (e.g., documentation of a named health care agent or completion of a living will) and/or MOLST/MOST who also have a textual reference to advance care planning-related conversations or documentation in the clinicians' note. Results will be examined in the aggregate by clinic site. We seek to understand the percentage of patients at each clinic who have engaged in an ACP-related encounter by whether they do or do not have documentation of their wishes.

For each of the 19 JHCP and 35 MedStar Health clinics that are part of this trial, we will randomly select 30 - 40 electronic health records of patients age 65 and older under the care of a clinician at the clinic for whom an advance directive has been documented in the electronic health record. Trained study staff at JHCP and MedStar Health will manually review the documented advance directive to confirm that the uploaded document is an advance directive, and, if so, whether the advance directive includes the naming of a health care agent only, the completion of a living will only, or both. The goal of the advance directive audit will be to identify the percentage of advance directives that are documented as being completed that are in fact an advance directive. We will additionally identify variability in the accuracy of advance directive completion by clinic, by patient age group, and for patients with and without a diagnosis of dementia.

Mailings

PHI from EPIC will be requested and disclosed to School of Public Health team members to access data on patients who may be eligible for the advance care planning services – this data will include name, age, primary care physician, upcoming appointments, and address. The team members will use this to identify patients who can receive the SHARING CHOICES intervention (over 65 and with an upcoming appointment in primary care clinics randomized to SHARING CHOICES) and will use patient names and addresses in order to mail the information about the SHARING CHOICES components available in their clinic.

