9.2 Sample Size and Randomization

The unit of randomization for this study is the primary care practice. Practices will be stratified by health system and balanced on practice characteristics, including practice size, geographic location (urban, rural, suburban), and patient mix by race.

Practices randomized to control will continue to provide usual care. Practices randomized to SHARING CHOICES will provide usual care as well as the components of SHARING CHOICES. SHARING CHOICES will be available to all patients ages 65 and older who receive care at up to 33 practice sites.

9.3 Interim analyses and Stopping Rules: N/A.

9.4 Outcomes will include the rates of advance directive documents uploaded to the EHR (primary outcome), advance care planning documentation, and potentially burdensome care within the last six months of life.

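### Do the three practice counts (up to 100, 54 and up to 33) show that the trial's stated size is overstated?

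*Combined protocol and SAP*

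**What the plan says.** The number of practices appears in four places.

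- **Protocol summary, Sample Size and Population:** participants are patients aged 65 and over "at up to 100 primary care practices". The next sentence gives the expected patient numbers: "We anticipate that 9,200 of 87,000 of older patients will have a diagnosis of ADRD", with 7,000 deaths within 12 months of entry. It does not say how many practices these totals assume.
- **Section 3, Study Design:** outcomes are aggregated "in up to 100 diverse primary care practices from 2 health systems". The same paragraph describes a data-quality audit "across 19 JHCP and 35 MedStar clinics prior to the launch of the intervention".
- **Section 6, Study Procedures (Audit):** records are sampled "For each of the 19 JHCP and 35 MedStar Health clinics that are part of this trial".
- **Section 9.2, Sample Size and Randomization:** the intervention is open to older patients "who receive care at up to 33 practice sites". The section gives no total, no number per arm and no allocation ratio.

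Section 4 names the only source of practices: "Practices will be included from two health systems: Johns Hopkins Community Physicians (JHCP) and MedStar Health". It adds that randomization is stratified by system and balanced on clinical characteristics. Section 9.1 is marked as not applicable. No section gives a significance level, power, target difference, control rate or intracluster correlation.

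**The concern.** In a cluster trial whose outcomes are assessed by practice (Section 6, Outcomes), the number of practices largely determines the standard error. A reader meets 100 in the summary and in Section 3, then finds that the clinics the protocol counts as its own number 54. The natural inference is that 100 is left over from a more ambitious plan and that the trial is little more than half the advertised size.

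The cap of 33 adds to the unease. With 100 practices it means roughly one intervention practice to two controls. With 66 it means equal arms. With 54 it means anything up to 33:21. The protocol does not say which applies.

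Two things could be at stake. Someone judging precision from 100 practices would expect a smaller standard error than 54 can give. And if the 87,000 patients, 9,200 with ADRD and 7,000 deaths were built on 100 practices, the true numbers could be close to half of those. The decedent count matters most here, because the end-of-life outcome is measured only in patients who die.

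**Working it through.** **Inputs.** Ceiling of 100 practices (summary; Section 3). 19 JHCP and 35 MedStar clinics (Sections 3 and 6). Ceiling of 33 intervention sites (Section 9.2). 87,000 patients, 9,200 with ADRD and 7,000 deaths (summary).

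**1. Count.** 19 + 35 = 54. This does not reproduce 100, but it does not breach a ceiling of 100 either.

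**2. What the cap of 33 permits.**

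| Total practices | Split | Within the cap? |
|---|---|---|
| 100 | 50:50 | No, 50 exceeds 33 |
| 100 | 33:67 | Yes |
| 66 | 33:33 | Yes |
| 54 | 27:27 | Yes |
| 54 | 33:21 | Yes |

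The cap excludes equal allocation of 100 practices and nothing else in this list. It cannot show that the total is too high.

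**3. Choice of comparator.** Measured against 50:50, the standard error would be 1.36 times larger at 27:27 and 1.40 times at 33:21. The protocol's own cap excludes 50:50, so the fair reference for 100 practices is 33:67.

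**4. Standard error against 33:67.** Assume equal practice weights and equal between-practice variance. The standard error is then proportional to √(1/a + 1/b).

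- 33:67: √(1/33 + 1/67) = 0.2127
- 33:33: √(2/33) = 0.2462; ratio 0.2462/0.2127 = 1.16
- 27:27: √(2/27) = 0.2722; ratio 0.2722/0.2127 = 1.28
- 33:21: √(1/33 + 1/21) = 0.2791; ratio 0.2791/0.2127 = 1.31

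**5. Power, illustration only.** Suppose 33:67 had 80% power at two-sided 5%; neither figure is in the protocol. With the normal approximation the standardized effect is 1.960 + 0.842 = 2.802. Dividing by the ratios in step 4 (1.2798 and 1.3126 before rounding):

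- 27:27: 2.802/1.2798 = 2.189; Φ(2.189 − 1.960) = 59%
- 33:21: 2.802/1.3126 = 2.134; Φ(2.134 − 1.960) = 57%

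A noncentral t calculation gives 58% and 56%. Both versions ignore the stratification by health system.

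**6. Patient totals.** 87,000/100 = 870 per practice; 87,000/54 = 1,611 per practice. If the totals were built on 100 practices, 54 would yield 0.54 × 87,000 = 46,980 patients, 0.54 × 9,200 = 4,968 with ADRD and 0.54 × 7,000 = 3,780 deaths. If they were built on the 54 clinics, they stand as printed. The protocol does not say which.

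**The case for a change.** The best argument for a change is that a ceiling makes sense only while recruitment is open, and here the protocol already names a definite set of clinics. Section 4 draws practices from the same two systems only, and nowhere is it said that more will join. Section 10.3.1 says the audit is to assure data quality at all clinics, and the audit covers 54. So either further practices would go unaudited, or 100 does not describe this trial. A cluster trial that does not fix its number of clusters also leaves readers unable to judge its precision.

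Much of this stands. The three counts are not reconciled, the allocation ratio is absent, and 54 is the most likely number. Three points limit what follows.

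- The 54 comes from a description of a pre-launch audit. Sections 4 and 9.2, which cover randomization, give no total. The text also moves between clinics, practices and practice sites without saying that they are the same unit. That 54 practices are randomized is therefore a good inference, not a stated fact.
- The loss of precision needs a promise to be measured against, and the protocol makes none. The lack of a stated detectable difference is a separate matter from the inconsistency in counts.
- The patient totals appear only in the summary, in a sentence of their own. Whether they are too high depends on a basis that is not given.

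**Conclusion.** No change to the plan follows. The three counts are loosely stated and not reconciled, but they are compatible: 54 is below the ceiling of 100, and 33 bounds one arm only. The single combination they rule out is equal allocation of 100 practices, which the protocol never claims.

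The precision figures (standard error 1.28 to 1.31 times that of 33:67, and power of about 57% to 59% where 33:67 is assumed to have 80%) are correct on their assumptions. Those are equal practice weights, a common between-practice variance and a power level that the protocol does not state. They compare two sizes that the text allows and do not show a missed target. The near-halving of the patient totals depends in the same way on an unstated basis.

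What is missing is detail that the study team holds and that any report of the trial will contain: the practices randomized by system and arm, the ratio used, and the clinics behind the patient totals. Writing it down earlier would help a reader. It would not alter which practices are analysed, how they are compared, or the validity of the result on 54 practices.

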4 IDENTIFICATION OF PRIMARY CARE PRACTICES

(1) Practice Identification: Practices will be included from two health systems: Johns Hopkins Community Physicians (JHCP) and MedStar Health. For the purposes of this study, primary care is defined as adult internal medicine, family medicine, and geriatric medicine. Practices will be randomized to SHARING CHOICES or usual care, stratified by health system and balanced on clinical characteristics.

4.1 Facilitator Identification:

Facilitators will be social workers or trained lay facilitators who will be employees of the Johns Hopkins School of Medicine or JHCP. Facilitators will be provided 15 hours of initial training, and biweekly, one hour training sessions prior to the start of the trial. Training will include all components of SHARING CHOICES, including: certification in the Respecting Choices ACP curriculum, with specific attention to working with patients with ADRD and families; documenting and uploading advance directives; patient and family portal registration and use; ADRD resources; and facilitating family communication with the agenda-setting checklist. Training will be delivered and reinforced using traditional didactics, case scenarios and video conversations, and modeling and mentored role play (see Attachment A4 for the training agenda). ACP facilitator staff will participate in two 55-minute simulation sessions to assess training fidelity, communication skills and the key elements of an ACP conversation.

5 STUDY INTERVENTIONS

Components of SHARING CHOICES that will be implemented as part of routine primary care in implementation practices include:

- 1) an electronic notice or letter from the primary care practice introducing SHARING CHOICES, including ACP (attachment A1 and B1),

- 2) a person-family agenda-setting checklist to align patient and family perspectives regarding the role of the family member in primary care interactions and stimulate interest in ACP (attachment A3 and B2),
- 3) access to a trained and certified facilitator to lead ACP conversations within the practice, and distribution of AD forms (attachment A2 and A5),
- 4) information on registration for the patient portal (for patient *and* family) to enable and extend electronic interactions and information access to patients and their family (A6, B3), and
- 5) implementation support, education and resources about ADRD for practice staff, tailored to SHARING CHOICES practices.

6 STUDY PROCEDURES

Audit

Preparatory to the detailed audit, an exploratory analysis will be performed using Natural Language Processing (NLP) to determine the number of existing patient records with a textual reference to advance care planning processes and documentation. This analysis will not include patient identifiers. NLP will be used to identify the proportion of patients whose charts do and do not have official documentation of an advance directive (e.g., documentation of a named health care agent or completion of a living will) and/or MOLST/MOST who also have a textual reference to advance care planning-related conversations or documentation in the clinicians' note. Results will be examined in the aggregate by clinic site. We seek to understand the percentage of patients at each clinic who have engaged in an ACP-related encounter by whether they do or do not have documentation of their wishes.

For each of the 19 JHCP and 35 MedStar Health clinics that are part of this trial, we will randomly select 30 - 40 electronic health records of patients age 65 and older under the care of a clinician at the clinic for whom an advance directive has been documented in the electronic health record. Trained study staff at JHCP and MedStar Health will manually review the documented advance directive to confirm that the uploaded document is an advance directive, and, if so, whether the advance directive includes the naming of a health care agent only, the completion of a living will only, or both. The goal of the advance directive audit will be to identify the percentage of advance directives that are documented as being completed that are in fact an advance directive. We will additionally identify variability in the accuracy of advance directive completion by clinic, by patient age group, and for patients with and without a diagnosis of dementia.

Mailings

PHI from EPIC will be requested and disclosed to School of Public Health team members to access data on patients who may be eligible for the advance care planning services – this data will include name, age, primary care physician, upcoming appointments, and address. The team members will use this to identify patients who can receive the SHARING CHOICES intervention (over 65 and with an upcoming appointment in primary care clinics randomized to SHARING CHOICES) and will use patient names and addresses in order to mail the information about the SHARING CHOICES components available in their clinic.

Facilitator Processes and Procedures

For ensuring fidelity of skills and competency, adherence to the SHARING Choices protocol, communication skills, and key elements in an ACP conversation will be assessed via evaluation of interactions with standardized patients (SPs) (**D1, D2, D3**). The Facilitator Lead ([name]) and a Facilitator Evaluator will utilize the Advance Care Planning (ACP) Facilitator Evaluation Checklist (**E1, E2**), a short fidelity instrument adapted from SHARE (IRB00242431) and Respecting Choices®. This is a 35-item checklist instrument to evaluate how well the ACP meeting is organized, which ACP topics were addressed, how the ACP conversation will be documented, and effectiveness of communication between the facilitator and SP. Data from the ACP Facilitator Evaluation Checklist will be used to provide feedback to each facilitator and inform additional booster training for the facilitators.

Individuals trained to guide ACP conversations will be invited to provide oral consent (**C1, C2**) to have the results of their assessment used for research purposes. Prior to the simulated patient evaluation, oral consent will be collected remotely. The objectives, procedures, and a clear statement explaining risks and benefits of the study will be presented during this review. All consenting will be completed by research staff trained in human subject research and the study protocol. Research staff will be required to read the entirety of the oral consent scripts, allowing for any questions, comments, or concerns of prospective participants.

ACP discussions will include an initial meeting of up to 45 minutes with scheduling future contacts as needed. We expect meetings will most often occur at the primary care practice, but may also occur by phone or through telehealth, in the community, or at the individual or family residence. In the initial meeting the facilitator will follow a conversation guide and employ motivational interviewing techniques to evaluate readiness and facilitate uptake and adoption of SHARING CHOICES components. Subsequent meetings can occur through ad-hoc requests (by patients, family, clinicians, or staff), or triggers such as hospitalizations.

Outcomes

Outcomes from practices randomized to SHARING CHOICES will be compared to practices within the same system who are randomized to usual care. Outcomes will be assessed at the level of the practice. Control practices will continue to deliver their usual care practices with respect to ACP and agenda setting.

